2.4 Imaging Objectives

2.4.1 To compare the change in ¹⁸F-FLT PET/CT uptake (from baseline to post-neoadjuvant therapy) among patients with and without pathologic complete response.

2.4.2 To compare post-neoadjuvant ¹⁸F-FLT PET/CT uptake among patients with and without pathologic complete response.

2.4.3 To estimate an optimal threshold for prediction of pathologic complete response using i) change in ¹⁸F-FLT PET/CT uptake, and ii) post-neoadjuvant ¹⁸F-FLT PET/CT uptake.

2.4.4 To assess the correlation between change in ¹⁸F-FLT PET/CT uptake and change in Ki-67.

3. Selection of Patients

Each of the criteria in the checklist that follows must be met in order for a patient to be considered eligible for this study. Use the checklist to confirm a patient's eligibility. For each patient, this checklist must be photocopied, completed and maintained in the patient's chart.

In calculating days of tests and measurements, the day a test or measurement is done is considered Day 0. Therefore, if a test is done on a Monday, the Monday four weeks later would be considered Day 28.

ECOG-ACRIN Patient No. _____

Patient's Initials (L, F, M) _____

Physician Signature and Date _____

NOTE: CTEP Policy does not allow for the issuance of waivers to any protocol specified criteria (http://ctep.cancer.gov/protocolDevelopment/policies_deviations.htm). Therefore, all eligibility criteria listed in Section 3 must be met, without exception. The registration of individuals who do not meet all criteria listed in Section 3 can result in the participant being censored from the analysis of the study, and the citation of a major protocol violation during an audit. All questions regarding clarification of eligibility criteria must be directed to the Group's Executive Officer ([contact]) or the Group's Regulatory Officer ([contact]).

NOTE: Institutions may use the eligibility checklist as source documentation if it has been reviewed, signed, and dated prior to registration by the treating physician.

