3.1.2.4 Stage IIID

T4b N3b/c M0 (if 3c: at least 1 clinically evident node)
Yes _____ No _____

_____ 3.1.3 Patient must have measurable disease on baseline imaging scans, obtained within 4 weeks prior to registration as defined by RECIST in Section [6.1.3](#) and by the following criteria.

_____ 3.1.3.1 All melanoma tumors must be completely resectable as determined by a surgical oncologist or experienced melanoma surgeon prior to registration.

_____ 3.1.3.1.1 Extensive satellitosis or extensive in transit metastases are not considered completely resectable.

_____ 3.1.4 Patient must have BRAF V600 mutation positive based on report from CLIA certified laboratory.

_____ 3.1.5 Patient must be medically fit to undergo surgery.

_____ 3.1.6 Patient must have adequate bone marrow, organ function and laboratory parameters (labs must be obtained \leq 14 days prior to registration) as defined below:

_____ 3.1.6.1 ANC $\geq 1.5 \times 10^9/L$
ANC: _____ Date of Test: _____

_____ 3.1.6.2 Hemoglobin $\geq 8 \text{ g/dL}$ without transfusion
Hemoglobin: _____ Date of Test: _____

_____ 3.1.6.3 Platelets $\geq 100 \times 10^9/L$ without transfusion
Platelets: _____ Date of Test: _____

_____ 3.1.6.4 AST and ALT $\leq 2.0 \times$ Institutional ULN;
AST: _____ Institutional ULN: _____
Date of Test: _____
ALT: _____ Institutional ULN: _____
Date of Test: _____

_____ 3.1.6.5 Total bilirubin $\leq 1.5 \times$ Institutional ULN and $< 2 \text{ mg/dL}$; OR total bilirubin $> 1.5 \times$ Institutional ULN with indirect bilirubin $< 1.5 \times$ Institutional ULN
Total Bilirubin: _____ Institutional ULN: _____
Indirect Bilirubin: _____ Institutional ULN: _____
Date of Test: _____

_____ 3.1.6.6 Serum creatinine $\leq 1.5 \times$ Institutional ULN, or calculated creatinine clearance $> 50 \text{ mL/min}$ by Cockroft-Gault formula
Creatinine: _____ Institutional ULN: _____
Date of Test: _____

Creatinine Clearance: _____ Date of Test: _____

_____ 3.1.6.7 PT, INR, and PTT $\leq 1.5 \times$ Institutional ULN

PT: _____ Institutional ULN: _____

Date of Test: _____

INR: _____ Institutional ULN: _____

Date of Test: _____

PTT: _____ Institutional ULN: _____

Date of Test: _____

- _____ 3.1.7 Patient must have an ECOG Performance status 0-1.
- _____ 3.1.8 Patient must not have any prior treatment with BRAFi or MEKi.
- _____ 3.1.9 Patient must not have any evidence of distant metastases.
- _____ 3.1.10 Patient must be able to take oral medications.

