- _____ 3.1.11 Patient must not have any prior adjuvant therapy at this disease presentation; prior immune therapy (such as adjuvant interferon or checkpoint inhibitors) is permitted if date of registration is ≥ 6 months from last treatment
- _____ 3.1.12 Patient must not have any prior radiation to the site of evaluable disease.
- _____ 3.1.13 Patient must not have active infection requiring treatment with parenteral antibiotics.
- _____ 3.1.14 Patient must be able to lie still during the ^{18}F -FLT PET/CT scan for the duration of the imaging study (up to 1.5 hours), have no previous indication of allergic reaction to the radiotracer, and meet the size limits of the qualified PET/CT scanner.
- _____ 3.1.15 Patient must be participating in this study at an institution which has completed the ECOG-ACRIN defined PET/CT scanner qualification procedures and received ECOG-ACRIN PET Scanner approval as outlined in Section [4](#).
- _____ 3.1.16 Patient must not have active Hepatitis B, and/or active Hepatitis C infection given concerns for drug interactions or increased toxicities. Testing is not required.
- _____ 3.1.17 Patients known to be HIV positive are eligible if they have undetectable HIV viral load and stable and adequate CD4 counts ($\geq 500\text{mm}^3$) on screening labs provided they meet all other protocol criteria for participation and that there is no high risk drug interactions. See [Appendix X](#).
- _____ 3.1.18 Patient must not have other significant medical, surgical, or psychiatric conditions that in the opinion of the investigator may interfere with compliance, or make the administration of study medications hazardous.
- _____ 3.1.19 Patient must not have had previous or concurrent other malignancy with the following exceptions:

Rev Add2

_____ 3.1.19.1 Adequately treated basal cell or squamous cell carcinoma of the skin, in situ carcinoma of the cervix.

_____ 3.1.19.2 Other solid tumor: if treated and without evidence of recurrence for at least 2 years prior to date of registration.

_____ 3.1.20 Patient must not be pregnant or breast-feeding due to potential harm to an unborn fetus and possible risk for adverse events in nursing infants with the systemic antineoplastic medications, as well as surgery and radiation being used.
All patients of childbearing potential must have a blood test or urine study within 14 days prior to registration to rule out pregnancy.

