- 1 CBCs (with differential and platelet count) which includes WBC, ANC, Platelets, Hgb, and Hct required for protocol therapy must be done < 24 hours prior to the treatment cycle. PT, PTT, INR will be collected at screening. Additional labs and frequency as clinically indicated per investigator discretion. Screening labs will be obtained within the one-week period prior to administration of FLT. Chemistry labs include; Sodium, chloride, CO₂ or bicarbonate, potassium, creatinine, BUN, glucose, calcium, total protein, albumin, total bilirubin, AST, ALT, alkaline phosphatase, LDH. If patient data is available from clinical records in the appropriate time window, they need not be repeated for the scans.
- 2 All patients of childbearing potential must have a negative [blood test or urine test] within 14 days prior to study registration to rule out pregnancy. If the pregnancy test done at baseline is greater than 14 days prior to Day 1 of treatment, it should be repeated prior to initiating treatment. A pregnancy test must also be done prior to starting adjuvant treatment.
- 3 Patients will record medication use of Encorafenib and Binimatinib per scheduled visits. See [Appendix III](#).
- 4 A full ophthalmic examination will be performed by an ophthalmologist at baseline and include best corrected visual acuity, slit lamp examination, intraocular pressure, dilated fundoscopy. Ocular Coherence Tomography (OCT) will only be performed if clinically indicated at the discretion of the ophthalmologist. Examination of the retina is required, especially to identify findings associated with serous retinopathy and RVO. After baseline, patients should be assessed at every physical examination for visual complaints. Symptomatic patients should be referred for a full ophthalmic consultation. For patients with clinical suspicion of retinal abnormalities of any grade (e.g., serous retinopathy, RVO, photopsia, metamorphopsia, impairment of visual acuity), these additional assessments should be mandatory. Full ophthalmologic exam will be pursued as needed throughout the study as clinically indicated.
- 5 CK will be performed at the same time points as the hematology collections. Troponin may be drawn as clinically indicated for abnormal CK. Follow up for total creatine kinase (CK) $\geq 3 \times$ ULN will include weekly assessment of isoenzymes and myoglobin in blood/or urine, and troponin as applicable.

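### The exception limb of eligibility criterion 3.1.6.5 sets no numeric limit on total or direct bilirubin and so bypasses the limit in the first limb

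*Combined protocol and SAP*

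**What the plan says.** Section 3.1.6 opens with "Patient must have adequate bone marrow, organ function and laboratory parameters" and defines adequacy by the numbered limits beneath it. Criterion 3.1.6.5 has two limbs.

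- **Limb 1:** total bilirubin at most 1.5 x ULN and also below 2 mg/dL.
- **Limb 2:** "OR total bilirubin $> 1.5 \times$ Institutional ULN with indirect bilirubin $< 1.5 \times$ Institutional ULN".

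The checklist line under the criterion collects total bilirubin and "Indirect Bilirubin: _____ Institutional ULN". Text and form therefore name the same fraction, and there is no field for direct bilirubin. The scheduled chemistry panel (Section 7.1, footnote 1) ends with "total bilirubin, AST, ALT, alkaline phosphatase, LDH" and lists neither fraction.

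The note at the start of Section 3 rules out waivers: "all eligibility criteria listed in Section 3 must be met, without exception". Sections 6.1.2 and 9.1 make eligibility under Section 3 part of the definition of an evaluable patient.

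**The concern.** A two-limb laboratory criterion normally has a general limit and a bounded exception. Here the exception lifts the general limit and puts nothing in its place for total or direct bilirubin. A criterion meant to establish adequate organ function then fails to bound the quantity it screens.

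The stake is mainly safety. The binimetinib risk list (Section 5.5.1) includes hepatic failure and raised transaminases, and the encorafenib side effects (Section 8.2.13.1) include raised liver tests. The hepatic rows of Table 3 in Section 5.6 address AST/ALT only. The rows for other adverse reactions accept a return to pretreatment or baseline levels, so an abnormal value admitted at entry can become the reference for later decisions.

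There is a smaller stake for the analysis set. With no waivers, the literal wording decides who counts as eligible, and hence who is among the 39 evaluable patients.

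**Working it through.** The plan states no figure that depends on this criterion, so there is none to reproduce. The check is to apply the rule as written.

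**Notation and inputs.** T = total, D = direct and I = indirect bilirubin in mg/dL, with T = D + I (the usual laboratory identity, which the documents do not spell out). U = ULN for total, UI = ULN for indirect.

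- Limb 1: T <= 1.5 x U and T < 2.
- Limb 2: T > 1.5 x U and I < 1.5 x UI.
- Eligible if either limb is met.

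**Assumptions.** The documents give no ULN values. I take U from 1.0 to 1.5; UI = 0.8, 1.0 or equal to U; and normal direct bilirubin as at most 0.3. So 1.5 x U runs from 1.5 to 2.25, and 1.5 x UI from 1.2 to 2.25.

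**1. Raised direct fraction.** Take I = 0.5 and D = 2, 5, 10 or 20, so T = 2.5, 5.5, 10.5 or 20.5.

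- T > 1.5 x U: 2.5 exceeds even the largest threshold, 2.25.
- I < 1.5 x UI: 0.5 is below even the smallest threshold, 1.2.

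Limb 2 admits all four patients at every ULN tried. Since D = T - I and limb 2 does not limit T, D has no upper bound under this criterion.

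**2. Clear isolated indirect elevation.** Take D = 0.2 and I = 2.5, 3 or 4, so T = 2.7, 3.2 or 4.2.

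- Limb 1: 2.7 > 2.25, so it fails.
- Limb 2: 2.5 > 2.25, so the indirect condition fails.

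All three patients are excluded at every ULN tried.

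**3. Mild isolated indirect elevation.** Limb 1 passes any T within its own limits. Limb 2 can add a narrow band when the two ULNs are equal. At U = UI = 1.2 it needs T > 1.8 and I < 1.8; with D <= 0.3 that means T < 2.1, or 1.81 to 2.09 on a 0.01 grid. The band is at most 0.3 mg/dL wide. At U = 1.2 with UI = 1.0, I < 1.5 gives T < 1.8, so limb 2 adds nothing; the same holds with UI = 0.8.

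**4. What remains of the 2 mg/dL limit.** It applies only in limb 1. There it matters only if 1.5 x U >= 2, that is U >= 2 / 1.5 = 1.33. If U < 1.33 and I < 1.5 x UI, limb 1 covers T <= 1.5 x U and limb 2 covers T > 1.5 x U, so every total is eligible.

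**5. Reversal at a higher ULN.** Take U = 1.5, so 1.5 x U = 2.25, and I = 0.5.

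| Total | Direct | Limb 1 | Limb 2 | Result |
|---|---|---|---|---|
| 2.1 | 1.6 | fails (not below 2) | fails (not above 2.25) | excluded |
| 2.5 | 2.0 | fails | met (2.5 > 2.25; 0.5 < 1.5 x UI) | admitted |

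At the same indirect value, the higher total is the eligible one.

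**6. Effect on the design.** None of the inputs to the two-stage design in Section 9.3 (14 and 39 evaluable, boundaries 5 and 18, rates 33% and 57%) involves this criterion. An exact binomial calculation gives alpha 0.048, power 0.873 and early stopping 0.699 under the null, in line with Section 9.3.

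**The case against.** The strongest reply is that 3.1.6.5 does not stand alone. A patient entering through limb 2 must also have "AST and ALT $\leq 2.0 \times$ Institutional ULN" (3.1.6.4), PT, INR and PTT within 1.5 x ULN (3.1.6.7), fitness for surgery (3.1.5), no active hepatitis B or C (3.1.16, testing not required), and no condition that "in the opinion of the investigator may interfere with compliance, or make the administration of study medications hazardous" (3.1.18). This stands in part. A reader might infer that nothing else in Section 3 would stop a patient with a markedly raised direct fraction, and that goes too far. But these safeguards act through another analyte or through judgement. None puts a number on total or direct bilirubin.

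A second reply is that limiting indirect bilirubin may be deliberate. Sections 8.1.12 and 8.2.15 say that binimetinib is metabolized mainly through UGT1A1 and that encorafenib inhibits it. The documents do not link this to the exception, and it would not explain why direct bilirubin is left open. It does bear on another tempting inference: that the exception works backwards and the word indirect is a slip for direct. The documents never state what the exception is for, so the intended fraction cannot be read from them.

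Two further readings are too strong. The 2 mg/dL limit is bypassed rather than cancelled, because it still operates in limb 1 where the total ULN is at least 1.33 mg/dL. And not every isolated indirect elevation is excluded, because mild ones can pass.

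**Conclusion.** The point holds as a defect in the wording of one criterion and should be fixed. As written, limb 2 imposes no numeric limit on total or direct bilirubin, bypasses limb 1, and can make eligibility reverse as total bilirubin rises.

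The absence of a ceiling follows from the text and the identity T = D + I, and does not depend on any ULN. The worked values do rest on assumed ULNs. The reversal between 2.1 and 2.5 mg/dL needs a total ULN high enough for the 2 mg/dL limit to bite, and was shown at 1.5 mg/dL.

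The documents give no frequency for such patients. The other criteria may exclude some of them, and sample size, alpha and power do not change. This supports a clear correction but not a higher grading, and it does not support a claim about which fraction the sponsor meant.

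**What to change.** In the next amendment, reconcile the two limbs of 3.1.6.5 and the matching checklist field so that the exception no longer leaves bilirubin unbounded. The sponsor's safety group should decide which fraction and limit apply, or whether the exception stays at all; this review does not propose either. If a fraction remains in the criterion, the screening chemistry list in Section 7.1, footnote 1, should name it, since it now lists total bilirubin only.

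A simple check on the revised text is that, at a fixed indirect value, a higher total bilirubin never turns an ineligible patient into an eligible one.

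The cost is a brief amendment with a checklist change. A few patients who could now enter under limb 2 may become ineligible; the documents do not allow that number to be estimated. No change to the statistical sections is needed.

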4.1 Registration Information

The following information is to be provided at the time of registration:

4.1.1 Protocol Number

4.1.2 Site/Investigator Identification

- Institution CTEP ID
- Treating Investigator
- Consenting Person
- Site Registrar
- Network Group Credit
- Credit Investigator

4.1.3 Patient Identification

- Patient's initials (first and last)
- Patient's Hospital ID and/or Social Security number
- Patient demographics
 - Gender
 - Birth date (mm/yyyy)
 - Race
 - Ethnicity
 - Nine-digit ZIP code
 - Method of payment
 - Country of residence

4.2 Eligibility Verification

Patients must meet all of the eligibility requirements listed in Section [3.1](#).

4.3 Additional Requirements

4.3.1 Patients must provide a signed and dated, written informed consent form.

NOTE: Copies of the consent are not collected by the ECOG-ACRIN Operations Office – Boston.

NOTE: Participation in the optional biopsy and additional specimen collections, as outlined in the patient consent, must be offered to all patients.

4.3.2 Bio-specimens are to be submitted as outlined in Section [10](#).

Rev Add2

4.3.3 Study Specific Training:
Each site must ensure all relevant site personnel responsible for handling ¹⁸F-FLT in any manner have reviewed and completed the training on handling and use of FLT. A review of the FLT Investigator Brochure and completion of ECOG-ACRIN generated training related to tracer administration will be required and documented via a training log. This training will be completed as a site initiation webinar prior to activation of the site. Any change in staff will require training of appropriate designated staff and this can be done through a self-study module with slides available on CTSU.

4.3.4 The Primary Investigator Authorized User
The ordering of ¹⁸F-FLT should be done with a written order from the responsible authorized user, and administration of ¹⁸F-FLT should be performed by the authorized user or a qualified staff member under the authorized user's supervision (e.g. nuclear medicine technologist). Institutions should follow institutional practice for the injection of investigational radiopharmaceuticals.
Sites must be a qualified user and/or manufacturer of ¹⁸F-FLT prior or have access to obtaining ¹⁸F-FLT to site activation. A list can be found on the CTSU website, on the EA6183 protocol page under the "Miscellaneous" tab.

4.3.5 Medidata Rave
Medidata Rave is a clinical data management system being used for data collection for this trial/study. Access to the trial in Rave is controlled through the CTEP-IAM system and role assignments. To access Rave via iMedidata, site staff will need to be registered with CTEP and have a valid and active CTEP-IAM account; and assigned one of the following Rave roles on the relevant Lead Protocol Organization (LPO) or Participating Organization roster at the enrolling site: Rave CRA, Rave Read Only, Rave CRA (LabAdmin), Rave SLA, or Rave Investigator. Refer to <https://ctep.cancer.gov/investigatorResources/default.htm> for registration types and documentation required. To hold Rave CRA role or Rave CRA (Lab Admin) role, the user must hold a minimum of an AP registration type. To hold the Rave Site Investigator role, the individual must be registered as an NPIVR or IVR. Associates can hold read-only roles in Rave. Upon initial site registration approval for the study in RSS, all persons with Rave roles assigned on the appropriate roster will be sent a study invitation e-mail from iMedidata. To accept the invitation, site users must log into the Select Login (<https://login.imedidata.com/selectlogin>) using their CTEP-IAM user name and password, and click on the "accept" link in the upper right-corner of the iMedidata page. Please note, site users will not be able to access the study in Rave until all required Medidata and study specific trainings are completed. Trainings will be in the form of electronic learnings (eLearnings), and can be accessed by clicking on the link in the upper right pane of the iMedidata screen. If an eLearning is required and has not yet been taken, the link to the eLearning will appear under the study name in iMedidata instead of

the Rave EDC link; once the successful completion of the eLearning has been recorded, access to the study in Rave will be granted, and a Rave EDC link will display under the study name.

Users that have not previously activated their iMedidata/Rave account at the time of initial site registration approval for the study in RSS will also receive a separate invitation from iMedidata to activate their account. Account activation instructions are located on the CTSU website, Rave tab under the Rave resource materials (Medidata Account Activation and Study Invitation Acceptance). Additional information on iMedidata/Rave is available on the CTSU members' website under the Rave tab at www.ctsu.org/RAVE/ or by contacting the CTSU Help Desk at [name] or by e-mail at [contact].

4.3.6 Data Quality Portal

The Data Quality Portal (DQP) provides a central location for site staff to manage unanswered queries and form delinquencies, monitor data quality and timeliness, generate reports, and review metrics.

The DQP is located on the CTSU members' website under Data Management. The Rave Home section displays a table providing summary counts of Total Delinquencies and Total Queries. DQP Queries, DQP Delinquent Forms and the DQP Reports modules are available to access details and reports of unanswered queries, delinquent forms, and timeliness reports. Review the DQP modules on a regular basis to manage specified queries and delinquent forms.

The DQP is accessible by site staff that are rostered to a site and have access to the CTSU website. Staff that have Rave study access can access the Rave study data using a direct link on the DQP.

To learn more about DQP use and access, click on the Help icon displayed on the Rave Home, DQP Queries, and DQP Delinquent Forms modules.

NOTE: Some Rave protocols may not have delinquent form details or reports specified on the DQP. A protocol must have the Calendar functionality implemented in Rave by the Lead Protocol Organization (LPO) for delinquent form details and reports to be available on the DQP. Site staff should contact the LPO Data Manager for their protocol regarding questions about Rave Calendaring functionality.

4.3.7 Image Data Submission Using TRIAD

TRIAD is the American College of Radiology's (ACR) image exchange application. TRIAD provides sites participating in clinical trials a secure method to transmit DICOM formatted image data, RT data and other objects. TRIAD anonymizes and validates the images as they are transferred.

TRIAD Access Requirements:

- Site staff that will be submitting images via TRIAD will need to register with CTEP and have a valid and active

CTEP-IAM account. Must be registered as an Associate, Associate Plus, Non-Physician Investigator, or Investigator registration type. Refer to the [CTEP](#) Registration Procedures section for instructions on how to request a CTEP-IAM account and complete registration in Registration and Credential Repository (RCR).

- To submit images, site staff must hold the TRIAD Site User role on an NCTN or ETCTN roster. Individuals requiring a TRIAD Site User role should contact the person holding a primary role at the site for their affiliated NCTN or ETCTN roster.
- All individuals on the Imaging and Radiation Oncology Core provider roster have access to TRIAD, and may submit images for credentialing purposes, or for enrollments to which the provider is linked in OPEN.

TRIAD Installations:

When a user applies for a CTEP-IAM account with the proper user role, he/she will need to have the TRIAD application installed on his/her workstation to be able to submit images. TRIAD installation documentation can be found by following this link <https://triadinstall.acr.org/triadclient/>.

This process can be done in parallel to obtaining your CTEP-IAM account username and password and RCR registration.

If you have any questions regarding this information, please send an e-mail to the TRIAD Support mailbox at [contact] or [[name]]([contact]).

Required Submission of Images for EA6183 via TRIAD

- Baseline ¹⁸F-FLT Whole Body PET/CT
- Week 8 ¹⁸F-FLT Whole Body PET/CT scan. Scan should take place after all neo-adjuvant treatment is completed and before surgery.
- All Standard of care ¹⁸F-FDG PET/CT imaging acquired

